6.2.6 Prior and Concomitant Antiepileptic Treatment

Treatments (collected on the prior/concomitant antiepileptic treatment eCRF page) will be coded using the World Health Organization Drug Dictionary (WHO-DD).

Prior and concomitant antiepileptic will be defined and analyzed for the SAF similar to concomitant medications as described in [section 6.2.5](#).

All prior and concomitant antiepileptic treatments will be listed for the SAF population.

6.2.7 Medical History

Medical history will be summarized and sorted alphabetically, by primary System Organ Class and Preferred Term coded using the most recent version of Medical Dictionary for Regulatory Activities (MedDRA). The number and percentage of subjects will be displayed for each System Organ Class and Preferred Term within treatment group.

Medical history will be presented for the SAF population.

All prior and concomitant medical history data of subjects will be listed for the SAF population.

6.3 EFFICACY ANALYSES

The analysis of the primary and secondary efficacy parameters will be performed on the mITT population, except where noted.

The primary and key secondary efficacy analyses will be repeated on the PP Population, in order to assess the impact of major protocol deviations on the key inference.

All primary and key secondary variables will be analyzed for data obtained for the T+M period, and will be repeated for data obtained during the M period only.

6.3.1 Primary Efficacy Analysis

The primary efficacy endpoint is the change in the mean convulsive seizure frequency (MCSF) per 28 days between the Baseline and T+M periods. For each subject, the convulsive seizure frequency (CSF) will be calculated from all available data collected during the Baseline and T+M Periods, and the treatment group MCSF per 28 days (MCSF) will be calculated for the baseline and T+M period.

The baseline period is the 42 days immediately preceding the Randomization visit and the T+M period is planned for 15 weeks (including 3 weeks titration). However, actual durations will be computed for each subject based on the individual subject's start and stop dates for each period with the exception that if the baseline period is longer than 42 days, the average for the baseline period will be the 42 days' data immediately preceding the Randomization date.

The convulsive seizure frequency will be counted from the daily diary records provided by the Subject or Parent/Caregiver.

For any individual subject, the convulsive seizure frequency per 28 days during the baseline period (CSF_B) will be derived as follows:

$$CSF_B = \frac{28 \times \text{Total number of convulsive seizures during the Baseline Period}}{\text{Total number of days in the Baseline Period with nonmissing diary data}}$$

For each treatment group, the mean is obtained by averaging over the subjects in the treatment group.

Similarly, for each subject, the convulsive seizure frequency per 28 days for the T+M period (CSF_{T+M}) is derived as below:

$$CSF_{T+M} = \frac{28 \times \text{Total number of convulsive seizures in the T + M period}}{\text{Total number of days in the T + M period with nonmissing diary data}}$$

The percentage change from baseline for any individual subject will be estimated by

$$(CSF_{T+M} - CSF_B) * 100 / CSF_B$$

The difference from baseline will be estimated by CSF_{T+M} – CSF_B.

Corresponding treatment group means are designated with “M” preceding the quantity. For each treatment group, descriptive statistics for MCSF during baseline, T +M study period, as well as the differences and % changes from baseline, will include the number of observations, mean, standard deviation, median, minimum and maximum, overall and by age group (<6 years, ≥ 6 years).

6.3.1.1 Primary Analysis Tests

T + M Period:

The primary analysis will compare the ZX008 0.5 mg/kg/day group to the placebo group using a two-sided test at $\alpha = 0.05$ level of significance.

The primary endpoint (CSF_{T+M}) will be analyzed using an analysis of covariance (ANCOVA) model with treatment group (ZX008 or Placebo) and age group (< 6 years, ≥ 6 years) as

classification factors, log baseline frequency (CSF_B) as a covariate in the model, and log CSF_{T+M} as response. Treatment group means and the difference from placebo will be estimated with least squares means from the analysis model along with 95% confidence intervals and associated 2-sided p-values. Estimated treatment group means and CI endpoints will be exponentiated for presentation.

The null hypothesis

$$H_0: \mu_{Z008} - \mu_P = 0,$$

will be tested against the alternative

$$H_A: \mu_{Z008} - \mu_P \neq 0,$$

where μ_{Z008} and μ_P represent the ZX008 0.5 mg/kg and Placebo group means (on the log scale), respectively.

Rejection of the null hypothesis in favor of the alternative, in the presence of a statistically significantly bigger reduction in mean convulsive seizure frequency from baseline for the treatment group compared to the placebo group, (two-sided p-value < 0.05) will be regarded as evidence of a treatment benefit in favor of ZX008 0.5 mg/kg group.

Sample SAS code for the ANCOVA described above is as follows:

```
proc glm data=temp;
  class agegrp trtp;
  model csftm = bcsf agegrp trtp / SS3;
  lsmeans trtp / pdiff stderr;
```

where trtp = randomized treatment group (with codes 1, 2 indicating placebo, and 0.5 mg groups).

bcsf = log(CSF_B),
csftm = log(CSF_{T+M})
agegrp = age group.

Additional statements may be used to obtain estimates and 95% confidence interval. Endpoints of the CIs may be exponentiated to obtain CI on the original scale. Fitted values and residuals may be plotted to check model assumptions.

Since the ANCOVA used in the primary analysis relies on assumptions of normality, the primary endpoint will also be analyzed using a nonparametric method that does not require as stringent assumptions. A nonparametric ANCOVA will be used to analyze the data, with ranks of the baseline CSF_B as a covariate and ranks of CSF_{T+M} as response. If normality assumptions are not met, the results of the nonparametric test will be used to assess the primary objective.

Treatment by Baseline Seizure Category:

The primary analysis described above will be repeated with baseline seizure frequency as a categorical variable, rather than a covariate.

Baseline seizure frequency per 28 days will be categorized as either < 10; 10-50; or >50

M Period only:

The primary analysis described above will be repeated using data from the Maintenance period only as response. For subjects who did not reach the Maintenance period, their Transition period data will be used to represent their M period data.

A similar ANCOVA model will be used, and if distributional assumptions are not met, a nonparametric analysis will be performed.

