5.1.3 Modified Intention-to-Treat (mITT) Population

The mITT Population is defined as all randomized subjects who receive at least one dose of ZX008 or placebo and for whom at least one week of diary data are available. Subjects will be analyzed according to the treatment group to which they were randomized. The primary comparison of ZX008 0.5 mg/kg/day to placebo, as well as key secondary analyses, will be performed on the mITT Population.

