6.1.7 Handling of Dropouts and Missing Data

There will be no imputation of missing data for efficacy endpoints.

Seizure Diaries:

Seizures are recorded in the Daily Seizure Diary (DSD), while the End of Day Diary (EDD) provides Yes/No confirmation that that seizures were experienced for a specific date, or that the date was seizure free.

- If no seizures are entered in the DSD and the EDD confirms seizure freedom, the number of seizures for that date is zero.
- If seizures are entered in the DSD and the EDD states seizure freedom, the seizures recorded for that date supersede the EDD stating seizure freedom.
- If no seizures are entered in the DSD and there is no response in the EDD, that day will be considered to have missing diary data.

- If no seizures are entered in the DSD and there is a Yes response in the EDD, that day will be considered to have missing diary data.

Unless specified otherwise in the relevant sections describing analyses for individual parameters, missing diary data will not be imputed for efficacy variables. Hence for subjects missing some of the daily measurements, the available data will be used. No explicit imputation will be performed for subjects who drop out prior to end of study (Visit 12).

Handling of missing date information for AEs:

- The term *missing date* refers to a completely missing date or to an incomplete date/partial date where parts are not available, e.g. missing month/day/year.
- Missing start and end dates will be imputed conservatively, i.e. missing values will be imputed in such a way that the duration of the AE is considered with the longest possible duration and such that, whenever the AE may potentially start after first IMP, the AE will be handled as a TEAE.
- The missing start date and End date of AE will be imputed for the purpose of calculating treatment emergent status and assigning events to treatment periods using definitions given in the following table.

Handling of missing date information for AEs:

- The term *missing date* refers to a completely missing date or to an incomplete date/partial date where parts are not available, e.g., missing month/day/year.
- Missing start and end dates will be imputed conservatively, i.e., missing values will be imputed in such a way that the duration of the AE is considered with the longest possible duration and such that, whenever the AE may potentially start after the first dose of IMP, the AE will be handled as a TEAE.

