6.3.1.2 Supplementary and Sensitivity Analyses

Per Protocol Analysis

Additionally, the primary efficacy analysis will be repeated on the per protocol population (which excludes subjects with important protocol deviations that may affect the inference on efficacy such as a change in dose or type of concomitant AED medication).

Percentage Reduction from Baseline

The ANCOVA employed in the primary analysis uses log CSF_{T+M} as the response and adjusts for baseline seizure frequency by incorporating CSF_B as a factor in the model. The alternative approach described here calculates the percentage change in CSF from baseline directly and uses that quantity as the response variable in an ANCOVA model. Specifically, the ANCOVA will use the percentage change from the T+M period as the response variable, baseline CSF as a covariate, and treatment and age stratum as classification factors. A parametric ANCOVA will then be used to compare ZX008 treatment group to placebo treatment group.

If the distributional assumptions for the parametric analysis are not met, a nonparametric ANCOVA based on the ranks as the dependent response variable, and using the ranks of the baseline as covariate will be used for the analysis.

Criteria for Establishing Efficacy

While several supportive and/or supplementary analyses are specified above, the main criterion for demonstrating efficacy will be the primary analysis for the mITT population. It is conceivable that some or all of the supplemental analyses may not reach statistical significance. However, it is expected that the direction of effect will be consistent in favor of ZX008 versus Placebo.

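### The deciding log-scale ANCOVA has no rule for CSF_T+M = 0; run literally in SAS it omits mITT subjects who had no convulsive seizure in T+M

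*SAP*

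**What the plan says.** - **Population.** SAP 5.1.3: "The primary comparison of ZX008 0.5 mg/kg/day to placebo, as well as key secondary analyses, will be performed on the mITT Population". Membership needs randomisation, a dose and a week of diary. There is no seizure requirement.
- **Endpoint.** SAP 6.3.1 computes CSF_T+M as 28 times "Total number of convulsive seizures in the T + M period", divided by the days in that period with diary data.
- **Zeros are data.** SAP 6.1.7: "If no seizures are entered in the DSD and the EDD confirms seizure freedom, the number of seizures for that date is zero". The missing-data rules therefore do not apply to a confirmed seizure-free day.
- **Model.** SAP 6.3.1.1 uses "log baseline frequency (CSF_B) as a covariate in the model, and log CSF_{T+M} as response". The variable definitions for the sample SAS code also take a plain log, with no added constant and no floor.
- **Fallback.** The same section says "Fitted values and residuals may be plotted to check model assumptions", and "If normality assumptions are not met, the results of the nonparametric test will be used to assess the primary objective". The fallback is a rank ANCOVA.
- **What decides.** SAP 6.3.1.2: "the main criterion for demonstrating efficacy will be the primary analysis for the mITT population". Under SAP 6.1.2 both key secondary tests depend on that result.

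**The concern.** A subject who becomes free of convulsive seizures on treatment has a valid result that the deciding model cannot use as written. The SAP expects such subjects elsewhere. Section 6.3.2.2 compares the arms on complete reduction, and 6.3.2.3 has a rule for a subject with no seizure. Protocol 10.5.1.1 describes an ANCOVA on change in seizure frequency, which can use a zero. The log enters only in the SAP, and SAP 6.9 does not list it as a change.

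At stake is what the primary ratio describes. If zeros drop out, it compares only subjects who still had seizures, selected by their outcome after randomisation. If a programmer instead supplies a constant or a floor, the choice was not pre-specified and moves both the estimate and the power.

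**Working it through.** **1. The plan's own figure.** Protocol 10.1 uses SD 58, difference 40, two-sided 0.05 and 90% power: n = 2 × (1.960 + 1.282)² × 58²/40² ≈ 44.2, so 45 per arm. It reproduces. It concerns percentage change and does not bear on zeros; the simulations below use 45 per arm.

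**2. Where the log fails.** With no seizure in 15 weeks (105 days), CSF_T+M = 28 × 0/105 = 0. SAS returns a missing value for log(0), and PROC GLM omits records with a missing response. This is standard software behaviour, not something the documents state. Baseline is safe: Protocol 4.3 requires at least 6 seizures in 6 weeks, so CSF_B is at least 28 × 6/42 = 4.

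**3. How many subjects.** The documents give no rate for T+M, so this is a range. For rate q on ZX008, the expected number omitted is 45q and the chance of at least one is 1 − (1 − q)^45.

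| q | expected omitted | chance of at least one |
|---|---|---|
| 2% | 0.9 | 60% |
| 5% | 2.25 | 90% |
| 10% | 4.5 | 99% |

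**4. Size by hand.** Assume a typical placebo value of 14 per 28 days, ratio 0.65 among subjects with seizures (0.65 × 14 = 9.1), and 10% zeros on ZX008 only.
- Deleted: 0.65.
- log(CSF+1): (10.1/15) × exp(−0.1 × ln 10.1) = 0.673 × 0.794 = 0.53.
- Half-seizure floor, 0.5 × 28/105 = 0.133: 0.65 × exp(0.1 × (ln 0.133 − ln 9.1)) = 0.65 × 0.656 = 0.43.

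**5. Simulation.** 4000 trials per scenario. Assumed: lognormal baseline (median 14, log SD 0.9) meeting the entry rule; Poisson counts over 105 days; between-subject log-response SD 0.8; age groups 50:50 with no age effect; ratio 0.65 among subjects with seizures. The two-step rule switches to the rank test at Shapiro-Wilk p<0.05. That threshold is an assumption made here, not the plan's.

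| Seizure-free, ZX008/placebo | Ratio: deleted | log(CSF+1) | floor | Two-step power: deleted | floor |
|---|---|---|---|---|---|
| 0/0% | 0.65 | 0.68 | 0.65 | 64% | 64% |
| 10/0% | 0.65 | 0.53 | 0.42 | 64% | 85% |
| 5/5% | 0.65 | 0.69 | 0.66 | 61% | 48% |
| 0/5% | 0.65 | 0.78 | 0.82 | 60% | 34% |

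Monte Carlo error is about 1 point on power and 0.01 on ratios. After deletion, Shapiro-Wilk fails in 10–11% of trials in all four rows. With zeros at the floor it fails in 15, 98, 99 and 90%. Deleted zeros therefore do not trigger the fallback, and retained zeros usually do.

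**6. Zeros from variable response only.** Baseline median 8, response SD 1.3, true ratio 0.40 and no separate seizure-free class give a mean of 1.4 zeros on ZX008 and 0.4 on placebo. Ratios are 0.42 deleted, 0.39 floor and 0.48 log(CSF+1). Power is 85% deleted and 87% for each of the others.

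**7. No treatment effect.** With ratio 1 (3000 trials), deletion followed by the two-step rule rejects in 5.1% (no seizure-free class), 4.6% (5% in each arm) and 5.2% (variable response).

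**The case against.** The best counter-argument is that the SAP never orders deletion. It assigns the comparison to the whole mITT population and offers its code only as a sample. On that set an undefined log could be read as failed normality, which leads to the rank ANCOVA, and that analysis keeps zeros and is produced in any case. This is a reasonable reading, but the SAP does not state it. The code would omit the records without comment, and the remaining residuals would give no sign of it. The percentage-change ANCOVA, the responder analysis and the comparison of complete reduction also keep zeros, so the information is reported, but none of them decides the primary objective.

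A second argument is that the harm is limited. At a ratio of 0.55, which gives 90% power when there are no zeros, two-step power at 10/0% is 89% with deletion and 97% with the floor. That stands: with a large effect the decision would seldom change.

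A reader might infer that deletion could manufacture a positive result. The documents do not support this. Protocol 1.1.1 describes seizure freedom on existing drugs as very uncommon. Protocol 1.6 reports 29 of 58 patient-years seizure-free on open-label fenfluramine. That evidence is uncontrolled and does not transfer directly to T+M, but it makes zeros likelier on ZX008. The 0/5% row, where deletion favours ZX008, is possible but less plausible, and the runs without a treatment effect show no type I error inflation.

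**Conclusion.** The point holds: 6.3.1.1 is wrong as written. The missing rule follows from the text alone. The omission follows from running that text literally in SAS. The normality fallback does not reliably repair it, because no check is named and zeros already deleted cannot influence it.

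The size is conditional on assumed seizure-free rates. At 10/0%, the ratio ranges from 0.65 to 0.42 according to a choice the SAP leaves open, with two-step power of about 64% (deletion) or 85% (floor). Deletion would more likely understate the benefit of ZX008 than overstate it. If zeros come only from variable response, it does little harm (0.42 against a true 0.40), and if no subject has a zero it does none. The simulations give every subject 105 diary days, so zeros from early dropout, which the one-week mITT rule permits, are untested.

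**What to change.** Before unblinding, amend the text and code of SAP 6.3.1.1:

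- State that no mITT subject is excluded because CSF_T+M is 0.
- Pre-specify one zero-retaining rule for the log response, such as a fixed constant or a half-seizure floor. The sponsor chooses it and fixes its value in advance. A constant on CSF_B is optional, since its log is already defined.
- Name a second rule as a sensitivity analysis, and report the planned rank ANCOVA alongside.
- Name the normality check and apply it to the model that includes the zeros.
- Apply the same rule to the maintenance-only, per-protocol and baseline-category repeats.
- Report the number of zeros per arm.

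This costs a few sentences and about two lines of code, with no new data. There are real downsides:

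- **The ratio depends on the rule.** log(CSF+1) gives 0.68 rather than 0.65 even with no zeros. A floor tied to diary days varies with follow-up: 0.5 × 28/7 = 2 per 28 days after one week, against 0.133 after 105 days.
- **Keeping zeros costs power if they are balanced.** At 5/5%, single-test power is 44% with log(CSF+1) against 62% with deletion.
- **The rank test, which gives no ratio, decides more often.** With log(CSF+1), Shapiro-Wilk fails in 51% of trials at 10/0% and 74% at 5/5%.

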10.5.1 Efficacy Analyses

The primary and key secondary efficacy analyses that compare ZX008 to placebo will be performed using subjects from Cohort 2 only. Efficacy endpoints, such as convulsive seizure frequency, assessed in Cohort 1 during the Transition Period will be summarized with descriptive statistics only.

10.5.1.1 Primary Efficacy Analysis – Cohort 2

The primary efficacy endpoint is the change in the mean convulsive seizure frequency (MCSF) per 28 days between the Baseline and T + M periods. The MCSF will be calculated from all available data collected during the Baseline or T + M Periods.

The primary endpoint will be analyzed using an analysis of covariance (ANCOVA) model with treatment group (ZX008 or placebo) and age group (< 6 years, \geq 6 years) as factors, and with baseline frequency as a covariate. The primary analysis will compare the ZX008 group to the placebo group using a two-sided test at the $\alpha=0.05$ level of significance.

Since the ANCOVA used in the primary analysis relies on assumptions of normality, the primary endpoint will also be analyzed using a nonparametric method that does not require as stringent assumptions. A nonparametric test will be used to compare the ZX008 group to the placebo group while stratifying for age group. If normality assumptions are not met, the results of the nonparametric test will be used to assess the primary objective.

Additional analyses will compare the percentage changes between the baseline MCSF and the MCSF measured independently during the Titration Period alone and the Maintenance Period alone.

10.5.1.2 Key Secondary Analyses – Cohort 2

The first key secondary endpoint – the proportion of subjects who achieve a $\geq 50\%$ reduction from baseline in convulsive seizure frequency – is derived directly from the primary endpoint. That is, the proportion of subjects in the ZX008 group who have a change in convulsive

frequency of at least 50 percentage points will be compared to the analogous proportion in the placebo group. The comparison will be made using a logistic regression model that incorporates the same factors and covariates as the ANCOVA used in the primary analysis. The analyses will be performed using data collected over the T + M period.

The longest interval between convulsive seizures will be calculated for each subject over the entire T + M period. The ZX008 and placebo groups will be compared using a Wilcoxon test.

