6.3.3.3 Change from Baseline in Non-Convulsive Seizure Frequency

Algorithms for calculating mean non-convulsive seizure frequency and change from baseline will follow the same methods as described for the primary endpoint.

Change from baseline in non-convulsive seizures will be presented by seizure types (e.g., absence, myoclonic).

The statistical comparison of treatment group and placebo will be done using a nonparametric ANCOVA similar to the method described in 6.3.1.1. Here the analysis will use the ranks of the non-convulsive seizure frequencies as the response variable, treatment as a factor, and the ranks of the baseline non-convulsive seizure frequencies as a covariate. Data will be displayed by treatment group as described for the primary endpoint.

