6.3.3.6 Incidence of Rescue Medication Usage

Use of rescue medication is recorded on the daily diary. In the event of prolonged seizures or status epilepticus, rescue medication is administered according to each subject's personalized regimen consisting of one or more medications. If the first rescue administration does not control the seizures, a second or even third round might be administered. The second and third round might use medications or doses different from the first round of rescue meds.

Rescue medication will be summarized by treatment group and by active treatment vs. Placebo for the following:

- The number of days rescue medication was taken (normalized to 28 days) will be summarized for the T + M period by the mean, standard deviation (SD), median and range. The ZX008 treatment group will be compared to the placebo group using a rank ANCOVA analogous to that described in [Section 6.3.1.1](#). Specifically, the ANCOVA will use ranks of rescue medication frequency during T+M as the response, and will incorporate treatment group as a classification factor and the ranks of rescue medication frequency during Baseline as a covariate.

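### The SAP's rank ANCOVA for the primary endpoint does not name the age stratum that the protocol's nonparametric test uses, and the rank ANCOVAs modelled on it list treatment as the only factor.

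*SAP*

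**What the plan says.** Protocol 10.5.1.1 specifies an ANCOVA for the primary endpoint with treatment and age group as factors and baseline frequency as covariate. For the nonparametric alternative it says: "A nonparametric test will be used to compare the ZX008 group to the placebo group while stratifying for age group". It then gives that alternative a possible deciding role: "If normality assumptions are not met, the results of the nonparametric test will be used to assess the primary objective".

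SAP 6.3.1.1 repeats the switch rule. Its parametric model includes age group in the text and in the sample code: "model csftm = bcsf agegrp trtp / SS3". The nonparametric version is described in one sentence, without code: "A nonparametric ANCOVA will be used to analyze the data, with ranks of the baseline CSF_B as a covariate", the response being the ranks of the T+M frequency.

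SAP 6.3.1.2 follows the same pattern for percentage change. The parametric model has treatment and age stratum, and the rank fallback mentions only a ranked response, "using the ranks of the baseline as covariate will be used for the analysis".

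SAP 6.3.3.3 (non-convulsive seizures) describes its method as similar to 6.3.1.1 and lists the terms as "treatment as a factor, and the ranks of the baseline non-convulsive seizure frequencies as a covariate". Section 6.3.3.4 repeats that sentence, 6.3.3.5 refers back to it, and 6.3.3.6 (rescue medication) "will incorporate treatment group as a classification factor and the ranks of rescue medication frequency during Baseline as a covariate".

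SAP 6.9 lists the changes from the protocol. Age stratification of the nonparametric test is not among them.

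**The concern.** The nonparametric test is more than supportive. If normality is judged to fail, it decides the primary objective. Under the serial hierarchy in Protocol 10.5.1.3 and SAP 6.1.2 it then also controls whether the two key secondary endpoints are formally tested. Its terms should be fixed before unblinding. As written, one analyst could fit the rank model with age group and another without it, and both could claim to follow the SAP.

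Age is also the stratification factor. Protocol 3.5 justifies it on the ground that younger subjects can have more frequent and more severe major seizures. Leaving the stratum out of the model puts any age effect not captured by baseline into the residual, which costs precision.

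**Working it through.** **1. Model terms, side by side**

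| Place | Analysis | Terms named |
|---|---|---|
| Protocol 10.5.1.1 | Primary, ANCOVA | treatment, age group, baseline |
| Protocol 10.5.1.1 | Primary, nonparametric | treatment comparison, stratified by age group |
| SAP 6.3.1.1 | Primary, log ANCOVA | treatment, age group, log baseline |
| SAP 6.3.1.1 | Primary, rank ANCOVA | ranked baseline, ranked response |
| SAP 6.3.1.2 | Percentage change, ANCOVA | treatment, age stratum, baseline |
| SAP 6.3.1.2 | Percentage change, rank version | ranked baseline, ranked response |
| SAP 6.3.3.3, 6.3.3.4 | Rank ANCOVA | treatment, ranked baseline |
| SAP 6.3.3.5 | Rank ANCOVA | refers to the model of 6.3.3.3 |
| SAP 6.3.3.6 | Rank ANCOVA | treatment, ranked baseline |

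The sentences in 6.3.1.1 and 6.3.1.2 are incomplete: they name neither treatment nor age. Those in 6.3.3.3, 6.3.3.4 and 6.3.3.6 do list the factor, and it is treatment alone.

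**2. Trial size used for the check**

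No stated figure in the plan depends on this model term. Protocol 10.1 gives 45 per arm (SD 58, difference 40 points, two-sided 0.05, 90% power). This reproduces: n = 2 × (1.960 + 1.282)² × 58² / 40² = 2 × 10.51 × 2.1025 = 44.2, so 45 per arm. Power at 45 is 90.5% by the normal approximation and 89.9% by the t distribution. SAP 6.1.10 states 40 per arm, which is a separate matter.

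**3. Effect of omitting age, by simulation**

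The documents give no residual age effect and no log-scale SD, so these inputs are assumptions:
- 45 per arm, allocated 1:1 within age strata, with half the subjects in each stratum
- normal errors with log-scale residual SD 0.8
- treatment effect 0 (type I error) or 0.45 log units (power), the latter a ratio of exp(−0.45) = 0.64
- age effect beyond baseline of 0 to 1.0 log units
- rank ANCOVA fitted with and without age group, two-sided 0.05, 4000 trials per setting

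| Residual age effect (fold difference) | Type I error, without / with age | Power, without / with age | Power cost (points) | Models disagree on significance (treatment effect present) |
|---|---|---|---|---|
| 0 (1.00) | 5.4% / 5.3% | 69.5% / 69.3% | −0.2 | 0.6% |
| 0.3 (1.35) | 4.8% / 5.1% | 69.1% / 70.4% | 1.3 | 1.7% |
| 0.6 (1.82) | 3.7% / 4.5% | 65.1% / 69.4% | 4.3 | 4.6% |
| 1.0 (2.72) | 2.4% / 5.3% | 57.7% / 69.9% | 12.2 | 12.3% |

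The Monte Carlo standard error of a 5% rejection rate is √(0.05 × 0.95 / 4000) = 0.34 points, so no entry shows inflation. The unadjusted test becomes conservative as the age effect grows. Stratified allocation balances age between the arms, but the model still counts age variation as error.

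A second set with heavy-tailed t(3) errors, a true ratio of 0.62, 90 subjects and 6000 trials per setting gave power without / with age of 70.2% / 70.2% at 0, 69.4% / 70.3% at 0.3 and 65.4% / 69.6% at 0.6. The costs are 0, 0.9 and 4.2 points. The error scale of that set is not stated here, so it serves only as a cross-check. It agrees.

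**The case against.** The strongest objection is that nothing has been dropped. The rank sentence in 6.3.1.1 comes straight after a full specification and code that include age group, and can be read as stating only what changes, namely ranks in place of logs. It does not name treatment either, and nobody would fit it without treatment. The same holds for 6.3.1.2. Elsewhere the SAP keeps age: in the logistic regression for responders (6.3.2.1) and in the Cochran-Mantel-Haenszel tests for status epilepticus (6.3.3.8) and CGI-I (6.3.3.14). This stands as far as it goes: for the primary endpoint the text is ambiguous rather than a proven omission. The later sections that claim to follow 6.3.1.1 and list treatment alone weaken the shorthand reading but do not settle it, since they concern other endpoints.

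A reader might also infer that the SAP removes age from all its rank analyses. The documents do not support that. Seizure-free days (6.3.3.1) follow the primary analysis, and nothing there drops age. The longest seizure-free interval is compared by an unstratified Wilcoxon test in the protocol itself, so the protocol does not require every rank test to be stratified.

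Nor do the secondary rank ANCOVAs contradict the protocol. Its stratification sentence covers the primary endpoint only, and the endpoints in 6.3.3.3 to 6.3.3.6 lie outside the testing hierarchy.

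Finally, the loss is small unless age matters well beyond baseline. A residual effect of 0.6 log units is a 1.8-fold difference after baseline adjustment, and no document supports an effect of that size. This also stands.

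**Conclusion.** The point holds as a gap in specification. Taken literally, the SAP's fallback for the primary endpoint departs from Protocol 10.5.1.1 without a declaration in 6.9. Taken as shorthand, it still leaves the terms of a potentially deciding test unstated. For 6.3.3.3 to 6.3.3.6 the inconsistency is with the stratified design and the SAP's own primary model.

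It would be tempting to conclude that the fallback risks a false claim of efficacy. It does not: omitting age does not inflate type I error. The possible cost is power, and only if the fallback is triggered. With 90 subjects and power near 70%, that cost is about 0 to 1 point for a residual age effect of 0 to 0.3 log units and about 4 points at 0.6. It is larger only at more extreme values. These sizes rest on assumed error distributions, treatment effects and age effects, none of which the documents supply.

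**What to change.** In SAP 6.3.1.1, state that the rank ANCOVA has treatment and age group (<6, ≥6 years) as factors, ranked baseline frequency as covariate and ranked T+M frequency as response. A line of sample code like that given for the parametric model would remove any doubt. Carry age group into the rank fallback in 6.3.1.2 and, for consistency, into the rank ANCOVAs in 6.3.3.3 to 6.3.3.6. If age is meant to be left out of the primary fallback, list and justify that in 6.9.

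The cost is a phrase in each of six SAP sections, made before unblinding. It needs no new data and no change in sample size. In the simulations, including age group when it had no effect changed power by no more than 0.2 points. This is a free improvement.
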